6.3.2 Patient Demographics and Baseline Characteristics

Patient demographics, baseline characteristics, disease history, medical history, prior cancer therapy, and other collected baseline data will be summarized using descriptive statistics.

6.4 Study Drug Exposure and Concomitant Medications

Study drug exposure and concomitant medications will be summarized by descriptive statistics. The summary of study drug exposure will include descriptive statistics as well as frequency counts for the number of doses or cycles received, the total dose actually administered as well as the total dose intended, and the dose intensity which is calculated as percentage of total dose actually administered divided by total dose intended during whole treatment period.

Duration of study treatment (months) will be calculated as:

- $(\text{date decided to discontinue treatment} - \text{date of first dose} + 1) / (365.25/12)$ for patients who have discontinued treatment.
- $(\text{date of data cutoff} - \text{date of first dose} + 1) / (365.25/12)$ for patients whose treatment is ongoing.

The summary of concomitant medications will include the number and percentage of patients who receive any concomitant medications as well as each concomitant medication by drug class.

6.5 Subsequent Anti-Cancer Therapy

Anti-cancer therapies received after study drug discontinuation may include chemotherapy, immunotherapy, radiotherapy, and surgery. Number and percentage of patients with any subsequent anti-cancer therapy will be summarized.

6.6 Protocol Deviations

Major protocol deviations will be identified prior to database lock for final analysis and will be listed and summarized.

6.7 Efficacy Endpoint Analyses

6.7.1 Primary Efficacy Endpoints Analyses

Number and percent of patients with their BOR in the response evaluable population will be summarized. The ORR and its 2-sided 95% exact binomial CI will be calculated for each cohort.

6.7.2 Secondary Efficacy Endpoints Analyses

The Kaplan-Meier method will be applied to estimate PFS, DoR and OS curves, their median times, PFS rates at 6 and 12 months, and OS rates 12 and 24 months, respectively. The method of Brookmeyer and Crowley (1) will be used to construct 95% CI for median time of each time-to-event endpoint. The 95% CIs for PFS and OS rates at each time point of interest will be calculated by normal approximation after log(-log) transformation.

DCR and its 2-sided 95% exact binomial CI will be calculated in the response evaluable population.

6.7.3 Other Efficacy Endpoints Analyses

The tumor size percent change from baseline over time will be summarized and presented by spider plot. The best tumor size percent change from baseline prior to the date of first PD or initiation of new anticancer therapy will be presented by waterfall plot.

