14.6.2 Analysis of Tumor Size Change Over Time

The tumor size is defined as the sum of diameters of the target lesions. The tumor size change from baseline over time will be summarized and presented by spider plot. The best tumor size change from baseline will be presented by waterfall plot.

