2.3.1 Evaluation of target lesions

Complete Response (CR): Disappearance of all target lesions. Any pathological lymph nodes (whether target or non-target) must have reduction in short axis to < 10 mm.

Partial Response (PR): at least a 30% decrease in the sum of diameters of target lesions, taking as reference the baseline sum diameters.

Progressive Disease (PD): at least a 20% increase in the sum of diameters of target lesions, taking as reference the *smallest sum on study* (this includes the baseline sum if that is the smallest on study). In addition to the relative increase of 20%, the sum must also demonstrate an absolute increase of at least 5 mm. (*Note*: the appearance of one or more new lesions is also considered progression).

Stable Disease (SD): Neither sufficient shrinkage to qualify for PR nor sufficient increase to qualify for PD, taking as reference the smallest sum diameters while on study.

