3.1 Overall Study Design and Plan

This is a Phase 2, open label, non-randomized study in the first-line treatment of patients with recurrent or metastatic SCCHN not curable by local therapy, with no prior systemic therapy for SCCHN in the recurrent or metastatic setting (with the exception of systemic therapy completed > 6 months prior if given as part of multimodal treatment for locally advanced disease).

Approximately 80 patients will be enrolled in 2 cohorts, as shown in **Figure 1**, to receive enoblituzumab in combination with either retifanlimab (Retifanlimab Cohort, PD-L1 positive [CPS \geq 1] patients, N=50) or tebotelimab (Tebotelimab Cohort, PD-L1 negative [CPS < 1] patients, N=30). Enrollment into each cohort will occur in a non-randomized fashion. Patients may not crossover between cohorts. PD-L1 expression will be prospectively collected and prospectively analyzed. B7-H3 and LAG-3 expression will be prospectively collected and retrospectively analyzed.

Figure 1

Study Schema

[figure not shown]
Enrollment in the 2 study cohorts will occur independently in a non-randomized fashion

Dosing Regimens:
 Enoblituzumab: 15 mg/kg Q3W
 Retifanlimab: 375 mg Q3W
 Tebotelimab: 600 mg Q3W

Efficacy Outcomes
Primary: ORR
Secondary: PFS, DCR, DoR, OS

Patients will receive the assigned study drugs (enoblituzumab 15 mg/kg and either retifanlimab 375 mg or tebotelimab 600 mg) on a every 3 weeks (Q3W) basis, in cycles of 3 weeks duration (see **Figure 2**). The initial tumor assessment will occur at the end of Cycle 2 (i.e., after approximately 6 weeks), and at the end of every 3 cycles thereafter (i.e., approximately every 9 weeks). After receipt of the last dose of study treatment, patients will enter an Efficacy Follow-up Period and will be followed for survival.

Figure 2

An independent Data Safety Monitor (DSM), the Sponsor, and Investigators will maintain regular oversight of patient safety throughout the trial. In the Tebotelimab Cohort, toxicity will be evaluated by monitoring the occurrence and severity of DLTs in the first 12 patients (2 mini-cohorts of 6 patients each) through Cycle 2 Day 7.

The data for each of the Retifanlimab and Tebotelimab Cohorts will be analyzed upon completion of enrollment of each cohort, and after all patients in the applicable cohort have at least one tumor assessment, to inform whether to proceed with the study and to determine any modifications to the trial design.

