4 ANALYSIS POPULATIONS

The study analyses will be performed on the following populations:

- **Safety Population:** All patients who received at least one dose of any study drug. This population will be used for analyses of safety, PK, pharmacodynamics, and immunogenicity. It will also be used for summary of baseline data and analyses of PFS and OS.
- **Response Evaluable Population:** All patients who received at least one dose of any study drug and had baseline radiographic tumor assessment. This population will be used for summary of tumor assessment data and analyses of responses.

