6 STATISTICAL METHODOLOGY

6.1 General Considerations

Safety and efficacy summaries will be provided for each cohort.

Unless otherwise noted, the baseline value is defined as the most recent value collected prior to the date and time of the first dose of study treatment. Study Day 1 is defined as the first day of study drug administration.

Categorical data will be summarized by the number and percent of patients falling within each category. Continuous variables will be summarized by descriptive statistics, including mean, standard deviation, median, minimum, and maximum.

Time to event endpoints will be summarized by the number and percent of the event, median time and corresponding 95% confidence interval (CI), and event free rate and corresponding 95% CI at the specified time points of interest.

All data summaries and tabulations will be conducted using SAS[®] software Version 9.4 or higher.

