6.2 Missing Data

Data that are reported as missing will be treated as missing in all data summaries. Imputation rules for partially recorded dates, where complete dates are required to carry out an analysis, will be provided in the Statistical Programming Plan (SPP). In descriptive summaries for safety, observations that are spurious (extreme relative to the majority of the data) will not be altered or removed from the summary.

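### Read literally, the SAP's waterfall rule leaves patients whose first post-baseline scan is PD without a bar

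*SAP*

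**What the plan says.** SAP 6.7.3 defines the waterfall value as the "best tumor size percent change from baseline prior to the date of first PD or initiation of new anticancer therapy". The sentence before it sets no such limit for the other figure: "The tumor size percent change from baseline over time will be summarized and presented by spider plot". Protocol 14.6.2 sets none for the waterfall either: "The best tumor size change from baseline will be presented by waterfall plot".

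Four other provisions decide how the rule works:

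- **Scan schedule.** SAP 3.1 and Protocol 11.1.1 place the first on-treatment tumor assessment at the end of Cycle 2, about 6 weeks after the start. The following scans come about every 9 weeks.
- **Baseline.** Under SAP 6.1, "the baseline value is defined as the most recent value collected prior to the date and time of the first dose of study treatment".
- **Missing data.** SAP 6.2: "Data that are reported as missing will be treated as missing in all data summaries".
- **Population.** The Response Evaluable Population in SAP 4 requires one dose and a baseline scan. SAP 4 says of it: "This population will be used for summary of tumor assessment data and analyses of responses".

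**The concern.** The cut-off is set by the patient's own outcome. A patient who progresses at the first scan has one post-baseline measurement in the eligible period, and it falls on the PD date rather than before it. The rule discards that measurement and has nothing to put in its place. Patients who progress later keep at least one earlier scan and so keep a bar.

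The waterfall would then leave out response-evaluable patients because they did badly early. The spider plot from the same paragraph, and the BOR table from SAP 6.7.1, would include them. At stake is how fairly a descriptive figure shows target-lesion change in two open-label cohorts without a control.

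**Working it through.** The plan states no figure here, so the check applies the wording to the schedule and then sizes the effect under stated assumptions.

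**Step 1: a patient with PD at the first scan.**

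| Measurement | Date relative to first PD | Eligible under SAP 6.7.3? |
|---|---|---|
| Baseline scan | before first dose | No: it is the reference, not a change from baseline |
| Week-6 scan showing PD | on the PD date | No: not before it |
| Any later scan | after the PD date | No |

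No eligible value remains, unless an unscheduled scan was done before week 6. SAP 6.1 uses the same words, prior to, for baseline in a strictly-before sense, so a programmer would naturally code a strict inequality. The back-dating rule in Protocol Appendix 4 (special notes on response assessment) can add patients: an equivocal finding at week 6 that is confirmed at the next scan makes week 6 the PD date.

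**Step 2: which bars are lost.** By target lesions, PD requires "at least a 20% increase in the sum of diameters of target lesions" from the smallest sum, plus at least 5 mm. At a first scan that is an upward bar. Appendix 4 (2.3.3, 2.3.5 and Table A-1) also allows PD by new lesions or non-target progression whatever the target lesions do. Some lost bars would therefore be flat or downward.

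**Step 3: how many.** The documents give no rate of PD at the first scan.

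- Inputs: week 6 is 42/30.4375 = 1.38 months. The median PFS of 3.2 months is the figure in Protocol 2.2 for pembrolizumab monotherapy in CPS ≥ 1. The 2- and 4-month medians are assumed, to show a range. Planned sizes are 50 and 30.
- Assumption: exponential PFS, so the share with an event by week 6 is 1 − 0.5^(1.38/m), where m is the median in months.

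| Median m | Share with event by week 6 | Of 50 | Of 30 |
|---|---|---|---|
| 4.0 | 21% | about 11 | about 6 |
| 3.2 | 26% | about 13 | about 8 |
| 2.0 | 38% | about 19 | about 11 |

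These counts are an upper guide under the model. They include deaths before any scan, and those patients have no bar under any wording. Protocol 2.2 gives no median PFS for CPS < 1, so the column for 30 borrows a figure from a different population.

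**Step 4: direction.** Suppose S of N patients show shrinkage and d are dropped, of whom s had shrinkage. The plotted share is (S − s)/(N − d), which exceeds S/N whenever s/d is below S/N. For illustration only, take S = 20, N = 50 and d = 13, so the true share is 40%:

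- s = 0: 20/37 = 54%
- s = 3: 17/37 = 46%
- s = 6: 14/37 = 38%

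The plot flatters the result unless the dropped patients shrink about as often as everyone else, which is unlikely among early progressors.

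**The case against.** The strongest reply is that this is a loose phrase on a minor figure. The waterfall is listed among other efficacy displays and feeds no estimate or decision rule. A cut around PD has a proper purpose: Protocol 4.1 and 4.4 let some patients stay on treatment past radiographic progression, and values under a new therapy should not count. Protocol 14.6.2 is merely silent on a cut, and Protocol 14 says the SAP will govern, so the difference between the two documents is not in itself an error. The author may have meant up to and including first PD, and SAP 7 defers programming specifications to a separate programming plan that is not available here.

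Most of this stands, and it limits the point to the boundary day. It does not remove it. The SAP as written excludes the PD-date scan, no passage in either document restores it, and a correction in another document would leave the governing text wrong. Plotting these patients at 0% would keep the denominator, but neither document provides for that, and it would show progressors as unchanged.

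A reader might infer more than the documents support:

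- **That the largest upward bars are the ones removed.** Step 2 shows that some may be flat or downward.
- **That a 40% shrinkage share would read as 54%.** That needs an invented starting share and no shrinkage among those dropped.
- **That the waterfall is the main display of response depth, to be set against the earlier enoblituzumab plus pembrolizumab plot (Protocol Figure 3).** Neither document says so, and the cut used for that figure is not stated.

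**Conclusion.** The point holds on the literal wording and is worth correcting. Every response-evaluable patient with PD at the first post-baseline scan lacks an eligible waterfall value and, under SAP 6.2, a bar, barring an unscheduled earlier scan. The bias usually runs in the favourable direction, but its size cannot be fixed from the documents. The 21% to 38% range rests on an exponential curve, medians of 2 to 4 months and a count that includes early deaths.

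The consequence is confined to one descriptive figure. ORR, BOR, DCR and PFS, and the sample-size reasoning, do not change, and early progressors remain visible as PD in the BOR table.

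**What to change.** In SAP 6.7.3, define the waterfall value as the best (smallest) percent change from baseline among assessments dated on or before first PD and before any new anticancer therapy begins. Values after progression stay excluded, as they are now. Add a footnote giving the number of response-evaluable patients without a post-baseline target-lesion measurement, with the reason (for example, death before the first scan).

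The cost is one phrase, one inequality in the program and one footnote. The change will not always move the figure in the same direction. A patient whose PD is due to a new lesion while target lesions are shrinking would gain a downward bar or a longer one.

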6.8 Safety Endpoint Analyses

6.8.1 Adverse Events Analyses

Only TEAEs will be summarized. The following AEs will be provided in summary tables as well as displayed in listings:

- All AEs
- AEs with CTCAE severity \geq Grade 3
- Study drug related AEs
- Study drug related AEs with CTCAE severity \geq Grade 3
- SAEs
- Study drug related SAEs
- AEs that resulted in discontinuation of study treatment
- AEs that led to interruption of individual study drug
- Fatal AEs
- AEs of special interest (AESI)

All of these tables will display the number and percent of patients that experience the given event and will display events by MedDRA System Organ Class (SOC) and Preferred Term (PT). Events will be displayed alphabetically for SOC and in descending order of PT incidence within each SOC. An overall summary of AEs will display the number and percent of patients who experience at least one event of each of the above types.

6.8.2 Laboratory Values Analyses

Summaries of laboratory values will display descriptive statistics for numerically quantified labs. Summaries will be grouped by lab panel (hematology, blood chemistry, and urinalysis) and will be displayed by visit for each lab parameter. Shift tables may be produced.

6.8.3 Other Safety Endpoints Analyses

Summary of weight and baseline height will be provided.

ECGs will be collected and analyzed for evidence of cardiac toxicity, especially prolongation of QT interval. The following categories for QT interval corrected by Fridericia method (QTcF) and maximum post dose change from baseline QTcF interval (Δ QTcF) may be used in summary and shift tables:

QTcF: ≤ 450 msec, >450 to 480 msec, >480 to 500 msec, and >500 msec

Δ QTcF: ≤ 30 msec, >30 to 60 msec, and >60 msec

Vital signs and ECOG performance status will be summarized with descriptive statistics at each visit and time point where they are collected. The ECOG shift from baseline to highest score during the on-treatment period will be summarized.

6.9 Pharmacokinetic, Pharmacodynamic, and Immunogenicity Parameter Endpoints Analyses

PK Analysis

Single and multiple dose PK parameters, including but not limited to C_{\max} and C_{trough} , will be derived from serum concentration versus time data. PPK analyses will be conducted using data from this study alone or combined with data from other studies. PPK and exposure-response modeling will be performed. Analysis will be conducted separately for enoblituzumab, retifanlimab, and tebotelimab.

Pharmacodynamic/Biomarker Analysis

Summary statistics for pharmacodynamic parameters will be provided and/or may be presented graphically. Possible associations between changes in pharmacodynamic measures of interest and enoblituzumab, retifanlimab, and tebotelimab dose and exposure may be explored. The distributions of PD-L1, LAG-3, and B7-H3 expression will be examined. The potential associations between the biomarkers and clinical response will be explored.

ADA Analysis

The proportion of patients who are negative for study-drug specific ADA at baseline and become positive in this assay, the proportion of patients who are negative at baseline and remain negative, and those who have positive ADA at baseline that increases or decreases in titer over the course of treatment will be summarized. Analysis will be conducted separately for enoblituzumab, retifanlimab, and tebotelimab.

6.10 Subgroup Analyses

The primary efficacy endpoint ORR will be analyzed by the following subgroups (not limited to those listed below). A particular subgroup analysis will be performed only if there are enough patients in that subgroup to render the analysis meaningful. Further, depending on the outcomes of the trial, these listed subgroup analyses may not be performed, or additional subgroups may be added, for the purpose of CSR. The SAP will not be revised for these changes.

The subgroups are defined as:

- PD-L1 expression in Retifanlimab Cohort: $CPS \geq 20$, $CPS < 20$
- HPV p16 status: Positive, Negative
- ECOG performance status: 0, 1
- Smoking status: Current/Former, Never
- Disease status: Metastatic, Recurrent only

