6.2 Blinding

Not applicable. This is an open-label study.

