14.8 Other Assessments or Analyses

Additional analyses, if any, will be defined in the SAP.

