3.2 Sample Size

The total sample size is planned to be approximately 80 patients, with approximately 50 and approximately 30 patients in the Retifanlimab and Tebotelimab Cohorts, respectively.

Enrollment into the Retifanlimab and Tebotelimab Cohorts will occur independently in a non-randomized fashion.

The sample size for each cohort is primarily based on providing preliminary estimation of ORR. **Table 1** provides 2-sided 95% confidence intervals (CI) for a number of potential responses.

Table 1 Response Rates and 95% Confidence Intervals

Sample Size	Number of Responses	Response Rate (%)	95% Confidence Interval (%)
30	2	6.7	0.8 – 22.1
30	3	10.0	2.1 – 26.5
30	4	13.3	3.8 – 30.7
50	10	20.0	10.0 – 33.7
50	14	28.0	16.2 – 42.5
50	16	32.0	19.5 – 46.7

ORRs of 19% and 5% were observed in first-line SCCHN patients with CPS ≥ 1 and CPS < 1 , respectively, in pembrolizumab monotherapy. In the Retifanlimab Cohort, based on an exact binomial test, 50 patients will distinguish a favorable true ORR of 36% from an unfavorable rate of 19% with 91% power and a 1-sided type 1 error rate of 0.079. Thus, at least 14 responses out of 50 patients are to be achieved. In the Tebotelimab Cohort, 3 responses out of 30 patients will have 80% confidence that the true ORR is $> 5\%$ (the lower limit of 1-sided 80% CI for the response rate is $> 5\%$).

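### SAP 6.10 lets listed ORR subgroups be dropped or new ones added according to trial outcomes, with no post hoc label or reason required, which does not fit Protocol 14.8

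*SAP*

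**What the plan says.** SAP 6.10 opens with a list that is explicitly open-ended: "The primary efficacy endpoint ORR will be analyzed by the following subgroups (not limited to those listed below". The five factors are CPS at a cut of 20 (Retifanlimab Cohort only), HPV p16 status, ECOG status, smoking status, and metastatic versus recurrent-only disease.

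A size condition follows: "A particular subgroup analysis will be performed only if there are enough patients in that subgroup to render the analysis meaningful". No minimum number is given.

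The next sentence, introduced by *Further*, adds a second condition: "depending on the outcomes of the trial, these listed subgroup analyses may not be performed, or additional subgroups may be added", for the purpose of the study report. The section closes with "The SAP will not be revised for these changes".

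Protocol 14.8 says: "Additional analyses, if any, will be defined in the SAP". On blinding, Protocol 6.2 says: "Not applicable. This is an open-label study".

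The primary analysis is in SAP 6.7.1: "The ORR and its 2-sided 95% exact binomial CI will be calculated for each cohort".

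**The concern.** A subgroup list in an analysis plan fixes which results will be shown before anyone knows which look good. A size condition is compatible with that, because subgroup size does not depend on response. An outcome condition is not. It lets an unremarkable listed subgroup disappear and a striking unlisted one appear, both under the authority of the plan.

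What is at stake is how the subgroup ORRs in the study report can be read. A favourable rate in one patient type means less if its companions were left out because of their results, and the section asks for nothing in the report that would say so. The opportunity exists. The trial is open label with Investigator-assessed response, and SAP 3.1 has each cohort's data analysed once enrolment is complete and every patient has had a tumor assessment. Outcomes will be known before the report's subgroup tables are settled.

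**Working it through.** The issue is one of wording, so most of the check sets the texts side by side. The design figures come first, to show what is not affected.

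**1. Design figures (SAP 3.2).** Inputs: n = 50, success at 14 or more responders, unfavorable rate 0.19, favorable rate 0.36. The plan states: "50 patients will distinguish a favorable true ORR of 36% from an unfavorable rate of 19% with 91% power and a 1-sided type 1 error". The value it gives for that error is 0.079.
- Type I error = P(X ≥ 14 | n = 50, p = 0.19) = Σ C(50,k)·0.19^k·0.81^(50−k) for k = 14 to 50 = 0.0791.
- Power = P(X ≥ 14 | n = 50, p = 0.36) = 0.9097.
- Clopper-Pearson 95% interval for 14/50 = 16.2% to 42.5%, as in SAP Table 1. The other five intervals in that table also reproduce.
- Tebotelimab Cohort, 3/30: lower one-sided 80% limit = 5.16%, above 5% as stated.

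The design figures are correct. They use the whole cohort and contain no subgroup term, so SAP 6.10 cannot change them.

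**2. Is the outcome condition separate from the size condition?** The size sentence already allows omission when a subgroup is too small. If the next sentence meant the same thing it would be redundant. It starts with *Further*, names the trial's outcomes as the ground, and covers additions as well, which a size rule cannot do. It is a second, independent permission.

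**3. What does the section guarantee?** All five factors have two levels, and SAP 6.1 calls for efficacy summaries by cohort.
- Retifanlimab Cohort: 5 factors × 2 levels = 10 results.
- Tebotelimab Cohort: 4 factors × 2 levels = 8 results, because the CPS split does not apply.
- Total: 10 + 8 = 18.

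The size condition has no number and the outcome condition has no criterion, so none of the 18 is assured. The list is open, so no further factor is excluded.

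**4. SAP 6.10 against Protocol 14.8.** The Protocol places the definition of additional analyses in the SAP. SAP 6.10 allows a subgroup not named there to be added, and says that the SAP will stay unchanged. Such a subgroup is reported without being defined where the Protocol says it will be.

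**5. Does another section close the gap?**
- SAP 7 puts the list of tables and figures in the statistical programming plan, but bases that list on the analyses described in the SAP. Neither document says that the programming plan fixes the subgroups before data are seen.
- SAP 6.6 covers major protocol deviations, not departures from the analysis plan.
- No section requires a post hoc label for an added subgroup, or a reason for a dropped one.

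**The case against.** **A benign purpose is possible.** The sentence refers to the outcomes of the trial, not to subgroup results. If a cohort has very few responders, or the study stops after the cohort-level review, subgroup ORRs would say little. SAP 5.1.2 applies the same logic to DoR, which is analysed only with enough responders. This may well be the intent, but the sentence does not say so. A responder-count condition is easily written, as the DoR text shows, and it would not explain outcome-dependent additions.

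**The unrevised SAP preserves a record.** This stands. The five-factor list in SAP Version 1.0 remains as written, and comparing it with the report would show what was added or left out. A reader might infer that planned and result-driven subgroups could not be told apart; that is too strong. Revising the SAP after outcomes are known would blur the record further. What remains is that the report itself need carry no label and no reason.

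**The subgroups are descriptive.** This also stands. No test, alpha or decision rule attaches to them. With an exact interval shown, a small subgroup looks as imprecise as it is: 7/25 is 28%, with a 95% interval of 12% to 49%.

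**A multiplicity figure is tempting but measures something else.** Suppose a true ORR of 19% in all 50 patients and five independent binary factors, with the smaller level holding 30% to 50% of patients. None of these factor assumptions is in the documents. In simulation, at least one level shows 28% or more in about 48% to 57% of trials, against 7.9% for the whole cohort. This is the ordinary result of looking at several small listed subgroups. It would be the same if all five were always reported, so it does not measure what the outcome condition does.

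**Protocol 14.8 might be read leniently**, with the open list counted as the SAP's definition. A general permission does not define any particular analysis, so the two texts still need reconciling.

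**Conclusion.** The point holds as a reporting defect of modest weight that is worth correcting. SAP 6.10 states a rule under which listed subgroup ORRs can be omitted and others added because of the trial's outcomes. It requires neither a post hoc label nor a reason, and it does not fit Protocol 14.8. Its scope is the 18 listed cohort-by-level results, none of them assured, plus any number of additions. The documents support no numerical estimate of the resulting bias.

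Three further inferences are not supported. The text permits selection on results; it does not show that selection will occur or is intended. These subgroups are not the only planned look at who responds, since SAP 2.3 and 6.9 also plan to relate biomarkers to clinical response. Nothing in either document says that the subgroup results will determine who enters a later study; the stated use of the cohort-level data review is to decide on continuing or modifying this trial.

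The conclusion rests on two assumptions: that outcomes of the trial include response results, and that the programming plan, which is not among the documents, does not fix the subgroup list before data are seen. If it does, the practical risk is smaller, but the SAP wording and the mismatch with Protocol 14.8 remain.

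**What to change.** - Delete the outcome-dependent ground for omission from SAP 6.10.
- Report all five listed subgroups for each applicable cohort, each level with n, responders, ORR and exact 95% CI. Where a level falls below a minimum n fixed in advance, print the row marked as not done.
- Label any subgroup added after data are seen as post hoc in the study report, and list every departure from 6.10 there with its reason.
- Reconcile 6.10 with Protocol 14.8, for example by stating that subgroups not named in the SAP are post hoc and fall outside the planned analyses.

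The SAP need not be revised once outcomes are known; the record of changes belongs in the report. Exploratory additions remain possible.

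The cost is a few sentences and one table of up to 18 rows, with no change to design, sample size or patient care. The downside is that some rows will be uninformative, particularly in the Tebotelimab Cohort of about 30 patients.
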